**4.2 Components of the Investigational Device System** 

# **4.2.1 Continuous Glucose Monitoring**

394 The study CGM will include an unmodified Dexcom G6 or G7 transmitter and sensors. This is an FDA-

approved device system for children as young as 2 years of age, with no changes to its hardware or

firmware components. The CGM sensor will be replaced at least once every ten days. Participants will be

397 permitted to switch between G6 and G7 components during the study if needed.

## **4.2.2 Phone Runn**

4.2.2 Phone Running t:connect Mobile App

Study data upload from pump and CGM will be achieved using the t:connect Mobile App, which will be
 installed on the parent/participant's personal phone during the study. This is a commercially-available,
 FDA-cleared software app with no modifications.

- 402 **4.2.3 Blood Glucose Meter and Strips**
- Blood glucose levels will be measured using the CONTOUR Next One meter and strips in accordancewith the manufacturer's labeling.
- 405 **4.2.3.1 Blood Glucose Meter Testing**
- All study blood glucose meters will be QC tested with control solution prior to dispensation. A tested meter will not be used in a study if it does not read within the target range at each concentration per manufacturer labeling. The participant will be instructed to contact study staff for a replacement of the meter and test strips if there is a suspicion that the meter is not reading accurately at home.
- Participants will be instructed on when and how to perform blood glucose testing.
- Participants will be reminded to use the study blood glucose meter for all fingerstick blood glucose measurements.

• Participants will be given guidelines for treatment of low or high blood glucose

# 415 **4.2.4 Ketone Meter and Strips**

Blood ketone levels will be measured using the Abbott Precision Xtra meter and strips in accordance with the manufacturer's labeling. The blood glucose meter component of the Precision Xtra device will not be used.

# 419 **4.2.4.1 Blood Ketone Testing**

- All study blood ketone meters will be QC tested with control solution prior to dispensation. A
   tested meter will not be used in a study if it does not read within the target range at each
   concentration per manufacturer labeling. The participant will be instructed to contact study staff
   for a replacement of the meter and test strips if there is a suspicion that the meter is not reading
   accurately at home.
- Participants will be instructed on when and how to perform blood ketone testing.
- Participants will be reminded to use the study blood ketone meter for all fingerstick blood ketone measurements.
- Participants will be given guidelines for treatment of elevated blood ketones.

# 429 **4.2.5 Study Device Accountability Procedures**

- 430 Device accountability procedures will be detailed in the site procedures manual.
- 431 **4.3 Safety Measures**
- 432 **4.3.1 CGM Calibration**
- Throughout the study, participants will be instructed to calibrate the study CGM in accordance with manufacturer labelling.

## 435 **4.3.2 Pump Failure**

If the CGM signal becomes unavailable for more than 20 minutes consecutively, Control-IQ or closed loop will not operate to automatically adjust insulin. If the CGM is not connected, the system will revert to usual function of the pump and deliver insulin with the insulin dosing parameters programmed in the system for that individual. Resumption of closed-loop will occur automatically once CGM signal is available again.

- 440 If the study system is unable to activate Control-IQ for any reason, the pump will automatically revert to 441 preprogrammed basal insulin delivery without any need for instruction from the user.
- 442 If the pump detects a system error that does not allow it to operate, the Malfunction Alarm will display and 443 the participant will be instructed to contact Tandem Technical Support via the study team.

# 4.3.3 Hypoglycemia Threshold Alarm and Safety Protocol

445 During the course of the study, participants will be permitted to change the CGM low glucose threshold 446 alert setting on their device or mobile app, but will be instructed to choose a value no less than 70 mg/dL.

447 The t:slim X2 with Control-IQ system will issue a predictive hypoglycemia alert (Control-IQ Low Alert)

when the system predicts BG <70 mg/dL within the next 15 minutes (<80 mg/dL when exercise mode is

449 activated).

444

- 450 If the participant receives a Control-IQ Low Alert, a message appears on the user interface (UI) that is
- 451 accompanied by vibration followed by vibrations and/or sound if not acknowledged by the user in 5
- 452 minutes. This alert remains on the screen until acknowledged by the user. The user is prompted to test blood
- 453 sugar and treat with carbs.

### 454

470

# 4.3.4 Hyperglycemia Threshold Alarm and Safety Protocol

- During the course of the study, participants will be permitted to change this setting, but will be instructed to choose a value no greater than 300 mg/dL.
- If a participant receives a CGM hyperglycemia threshold alarm or notes that the CGM glucose is above
   the hyperglycemia threshold alarm value, confirmatory fingerstick testing will be performed if required
- 459 by CGM labelling.
- 460 If a participant's CGM reading is >300 mg/dL for over 90 minutes or  $\geq 400 \text{ mg/dL}$  at any point, or if
- 461 CGM reading is >250 mg/dL more than 3 hours after a meal, the participant took correction insulin, and
- 462 CGM didn't decrease by at least 50 mg/dL, the participant will be instructed to take the following steps:
- Inspect infusion site for problems.
- Perform a blood glucose meter check.
- If the blood glucose is >300 mg/dL, check for blood ketones with the study ketone meter.
- If the ketone level is  $\geq$ 1.0 mmol /L, contact study staff for further instructions, which may include replacing the insulin infusion set.
- If a participant administers correction insulin via insulin syringe, participants will be instructed to turn Control-IQ off for approximately four hours and notify the study team.

# 4.4 Participant Access to Study Device at Study Closure

- 471 Participants will return all insulin pump, CGM, and related supplies at their final visit. Participant may
- keep the study ketone meter and study glucometer and test strips if all study data have been downloaded
- and these devices are not marked for investigational use only.

| 474        | Chapter 5: Testing Procedures  |
|------------|---|
| 475        | 5.1 Laboratory Testing  |
| 476        | 1. HbA1c:   |
| 477        | • Sample collected within 3 days of closed-loop initiation.   |
| 478
479 | • Blood samples will be sent to the central laboratory for sample analysis using an NGSP approved method. |

# Chapter 6: Unanticipated Problem, Adverse Event, and Device Issue Reporting

482 **6.1 Unant** 

6.1 Unanticipated Problems

Site investigators will promptly report all potential unanticipated problems meeting the criteria below on
an eCRF. Sites overseen by the JCHR IRB must report Unanticipated Problems to the IRB within seven
(7) calendar days of recognition. For this protocol, an unanticipated problem is an incident, experience, or
outcome that meets all of the following criteria:

- Unexpected (in terms of nature, severity, or frequency) given (a) the research procedures that are described in the protocol related documents, such as the IRB-approved research protocol and informed consent document; and (b) the characteristics of the subject population being studied
- Related or possibly related to participation in the research (possibly related means there is a reasonable possibility that the incident, experience, or outcome may have been caused by the procedures involved in the research)
- Suggests that the research places participants or others at a greater risk of harm than was
   previously known or recognized (including physical, psychological, economic, or social harm)

The Sponsor also will report to the IRB all potential unanticipated problems not directly involving a specific site such as unanticipated problems that occur study-wide or at another participating entity such as a vendor. These instances must be reported to the JCHR IRB within seven (7) calendar days of recognition. The Director of the JCHR Human Research Protection Program (HRPP) will report to the appropriate regulatory authorities if the IRB determines that the event indeed meets the criteria of an Unanticipated Problem requiring additional reporting to fulfill the reporting obligations of the HRPP.

501 **6.2 Adverse Events** 

# **6.2.1 Definitions**

503 Adverse Event (AE): Any untoward medical occurrence (including laboratory findings) associated with 504 study procedures, the use of a device, biologic, or drug in humans, including any comparator used, 505 whether or not the event is considered related (i.e., irrespective of the relationship between the adverse 506 event and the device(s) under investigation).

507 To further clarify, an adverse event is any unintended disease or injury, or untoward clinically significant 508 clinical sign (including abnormal laboratory findings) in a research participant that manifests while in the

509 study if it was not present before enrolling in the study, or if it was present before enrolling, it has

510 increased in severity, frequency or type since enrolling in the study. For this purpose, a participant is

511 considered enrolled once the participant has signed the consent form. Reportable AEs for this protocol are

- 512 defined in section 6.2.2.
  - 513 Serious Adverse Event (SAE): Any untoward medical occurrence that results in any of the following 514 outcomes:
  - 515 Death.
  - A life-threatening adverse event; (a non-life-threatening event which, had it been more severe, 517 might have become life-threatening, is not necessarily considered a serious adverse event).
  - Inpatient hospitalization or prolongation of existing hospitalization.
  - A persistent or significant disability/incapacity or substantial disruption of the ability to conduct 520 normal life functions.

• A congenital anomaly or birth defect.

522 An important medical event that may not result in death, be life-threatening, or require hospitalization

- 523 may be considered serious when, based upon appropriate medical judgment, they may jeopardize the
- 524 patient or subject and may require medical and surgical intervention to prevent one of the outcomes listed
- 525 in this definition. Note: If either the Sponsor or investigator believes that the event is serious, the event
- 526 must be considered serious and evaluated by the Sponsor for expedited reporting. See 21 CFR 312 for 527 more information.
- 528 Unanticipated Adverse Device Effect (UADE): Any serious adverse effect on health or safety or any life-
- 529 threatening problem or death caused by, or associated with a device, if that effect, problem, or death was
- not previously identified in nature, severity, or degree of incidence in the investigational plan or
- application (including a supplementary plan or application), or any other unanticipated serious problem
- associated with a device that relates to the rights, safety, or welfare of participants (21 CFR 812.3(s)).
- 533 Adverse Device Effect (ADE): An adverse event related to the use of an investigational medical device.
- 534 This definition includes adverse events resulting from insufficient or inadequate instructions for use,
- deployment, implantation, installation, or operation, or any malfunction of the investigational medical
- device. This definition includes any event resulting from use error or from intentional misuse of the
- 537 investigational medical device. This includes comparator if the comparator is a medical device. (Note
- that an Adverse Event CRF is to be completed in addition to a Device Deficiency or Issue CRF, unless
- excluded from reporting as defined in section 6.3).
- 540 Comparator: Medical device, therapy (e.g., active treatment, normal clinical practice), placebo or no 541 treatment, used in the control group in a clinical investigation. (ISO 14155:2020)
- 542 Device Complaints and Malfunctions: A device complication or complaint is something that happens to a
- 543 device or related to device performance, whereas an adverse event happens to a participant. A device
- complaint may occur independently from an AE, or along with an AE. An AE may occur without a device
- 545 complaint or there may be an AE related to a device complaint. A device malfunction is any failure of a
- device to meet its performance specifications or otherwise perform as intended. Performance
- 547 specifications include all claims made in the labeling for the device. For cleared devices, the intended
- 548 performance of a device refers to the intended use for which the device is labeled or marketed (21 CFR
- 549 803.3). Note: for reporting purposes, sites will not be asked to distinguish between device complaints and
- 550 malfunctions.
- 551 Use Error: User action or lack of user action while using the medical device that leads to a different result
- than that intended by the manufacturer or expected by the user. Includes the inability of the user to
- complete a task. Use errors can result from a mismatch between the characteristics of the user, user
- interface, task or use environment. Users might be aware or unaware that a use error has occurred. An
- unexpected physiological response of the patient is not by itself considered a use error. A malfunction of a
- medical device that causes an unexpected result is not considered a use error. (ISO 14155:2020)
- **6.2.2 Reportable Adverse Events**
- 558 For this protocol, a reportable adverse event includes any untoward medical occurrence that meets one of 559 the following criteria:
- 560 1. An SAE as defined in section 6.2.1
- 561 2. An ADE, unless excluded from reporting in section 6.3
- 562 3. An AE as defined in section 6.2.1 occurring in association with a study procedure
- 4. An AE as defined in which leads to temporary or permanent discontinuation of a study device

- 5. An AE as defined in section 6.2.1 that affects the participant's ability to complete any study 565 procedures
- 566 6. An AE as defined in section 6.2.1 for which a visit is made to a hospital emergency department
- 567 7. Hypoglycemia meeting the reporting criteria in section 6.2.3
- 568 8. Hyperglycemia meeting the reporting criteria in section 6.2.4
- An AE as defined in section 6.2.1 considered to be related to either ineffective insulin (e.g.,
  insulin exposed to high temperature that loses potency), signs or symptoms related to insulin
  infusion, or changing of type of insulin related to an AE.
- Hypoglycemia and hyperglycemia not meeting the criteria below will not be recorded as adverse events.
  Skin reactions from sensor placement are only reportable if severe and/or required treatment.
- 574 All reportable AEs—whether volunteered by the participant, discovered by study personnel during
- 575 questioning, or detected through physical examination, laboratory test, or other means—will be reported
- 576 on an AE CRF online. Each AE CRF is reviewed by the Medical Monitor to assess safety and to verify
- 577 the coding and the reporting that is required.

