78 or to secure the insulin infusion sets for the continuous subcutaneous insulin infusion. If these reactions

occur, different adhesives or "under-taping" (such as with IV 3000, Tegaderm, etc.) will be tried, sites will 79

be rotated frequently, and a mild topical steroid cream or other medication may be required. 80

- 81 Whenever the skin is broken there is the possibility of an infection. The CGM and pump infusion sites are
- 82 inserted under the skin. It is possible that any part that is inserted under the skin may cause an infection.
- 83 These occur very infrequently, but, if an infection was to occur, oral and/or topical antibiotics can be used.
- 84 The risk of skin problems could be greater if you use a sensor for longer than it is supposed to be used.
- 85 Therefore, participants (and parents) will be carefully instructed about proper use of the sensor.

Data downloaded from the CGM, pump, and the home glucose and ketone meter will be collected for the study as measures of diabetes self-management behaviors. Some people may be uncomfortable with the researchers' having such detailed information about their daily diabetes habits.

89 **1.3.2 Known Potential Benefits** 

90 It is expected that this protocol will yield increased knowledge about the feasibility of using an AI-driven 91 algorithm to adjust pump therapy parameters for an automated closed-loop system to control the glucose 92 level. The individual participant may not benefit from study participation.

93 **1.3.3 Risk Assessment** 

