6.2.6 Severity (Intensity) of Adverse Events

The severity (intensity) of an adverse event will be rated on a three-point scale: (1) mild, (2) moderate, or
(3) severe. A severity assessment is a clinical determination of the intensity of an event. Thus, a severe
adverse event is not necessarily serious. For example, itching for several days may be rated as severe, but

653 may not be clinically serious.

649

- MILD: Usually transient, requires no special treatment, and does not interfere with the participant's daily activities.
- MODERATE: Usually causes a low level of inconvenience, discomfort or concern to the
   participant and may interfere with daily activities, but is usually ameliorated by simple
   therapeutic measures and participant is able to continue in study.
- SEVERE: Interrupts a participant's usual daily activities, causes severe discomfort, may cause discontinuation of study device, and generally requires systemic drug therapy or other treatment.
- 661 6.2.7 Expectedness

662 For a serious adverse event that is considered possibly related to study device/procedure, the Medical

- Monitor will classify the event as unexpected if the nature, severity, or frequency of the event is not consistent with the risk information previously described in the approved labelling of the Control-IQ study pump.
- 666 **6.2.8 Coding o**

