# 700 **6.3 Reportable Device Issues**

All UADEs and ADEs as defined in section 6.2.1 will be reported on both a Device Issue CRF and AE CRF, except for skin reactions from CGM sensor placement or pump infusion set placement that do not

703 require pharmacologic treatment.

Device complaints and device malfunctions will be reported except in the following circumstances. These
 occurrences are expected and will not be reported on a Device Issue CRF assuming criteria for a UADE
 or ADE have not been met:

- CGM sensor lasting fewer days than expected per manufacturer
- CGM tape adherence issues
- Pump infusion set insertion lasting fewer days than expected per manufacturer
- Battery lifespan deficiency due to inadequate charging or extensive wireless communication
- Intermittent device component disconnections/communication failures not requiring system
   replacement or workaround/resolution not specified in user guide/manual.
- Device issues clearly addressed in the user guide manual that do not require additional troubleshooting

715 Use error (as defined above) will only be reported on a device issue form if an Adverse Event results from 716 the error. In these cases, both a Device Issue and an Adverse Event form will be completed.

717 **6.4 Timing of Event Reporting** 

SAEs possibly related to a study device or procedure and UADEs must be reported by the investigator to the Sponsor within twenty-four (24) hours of the site becoming aware of the event. This can occur via phone or email, or by completion of the AE CRF and Device Issue CRF if applicable. If the AE CRF is not initially completed, it should be completed as soon as possible after there is sufficient information to evaluate the event. All other reportable ADEs and other reportable AEs should be submitted by completion on the respective CRF within seven (7) days of the site becoming aware of the event.

The Sponsor will notify all participating investigators of any adverse event that is serious, related, and unexpected. Notification will be made within ten (10) working days after the Sponsor becomes aware of the event.

- Each site principal investigator is responsible for reporting serious study-related adverse events and
- abiding by any other reporting requirements specific to his/her Institutional Review Board or Ethics
- 729 Committee. Where the JCHR IRB is the overseeing IRB, sites must report all serious, related adverse
- rain events within seven calendar days.

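### Protocol 6.2.2 and 6.3 set different reporting thresholds for sensor-site skin reactions, so a severe reaction managed without a drug may or may not reach the adverse device effect table

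*Protocol*

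**What the plan says.** Section 6.2.2 lists the criteria that make an adverse event reportable. Item 2 is "An ADE, unless excluded from reporting in section 6.3". After the list comes a separate sentence on skin: "Skin reactions from sensor placement are only reportable if severe and/or required treatment". It covers sensor sites only, and it names severity and treatment of any kind as alternatives.

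Section 6.3 requires ADEs to be entered on both the Device Issue form and the AE form, "except for skin reactions from CGM sensor placement or pump infusion set placement that do not" "require pharmacologic treatment". This covers sensor and infusion-set sites. Only drug treatment matters, and severity is not mentioned. The ADE definition in 6.2.1 also points to 6.3 for exclusions.

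Section 8.4.1 lists ADEs and the rate of any adverse event per 100 person-years among the additional safety endpoints, and 8.13 has all safety endpoints tabulated. SAP 5.1 repeats both endpoints and adds no rule for skin reactions.

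**The concern.** Two sections that a site would consult for the same event give different thresholds. A coordinator working from the 6.2.2 sentence would report a severe sensor-site reaction however it was managed. A coordinator working from 6.3 would not report it unless a drug was needed. An event that never reaches a form cannot be recovered at analysis, and nothing in the SAP settles which rule applies.

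The study exists mainly to gather safety data in children aged 2 to under 6, using body-worn devices. Skin reactions are a named risk (1.3.1.7). What is at stake is whether the ADE table and the any-AE rate mean the same thing at each of the roughly three sites, and whether a severe device-site reaction can be missing from them.

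**Working it through.** The plan gives no figure on this point, so there is none to reproduce. The check has two parts.

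**1. The two rules side by side, sensor site.** The 6.2.2 column takes the skin sentence as implying that a reaction meeting its condition is reportable.

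| Severe? | Management | 6.2.2 sentence | 6.3 |
|---|---|---|---|
| No | none | not reportable | excluded |
| No | non-drug | reportable, if this is treatment | excluded |
| No | drug | reportable | reportable |
| Yes | none | reportable | excluded |
| Yes | non-drug | reportable | excluded |
| Yes | drug | reportable | reportable |

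The rules differ in 3 of 6 cells. Two of these, severe without a drug, follow from the wording alone. The third depends on what counts as treatment.

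The protocol leaves room for all three. Section 6.2.6 says that a severe event "generally requires systemic drug therapy or other treatment", so severe does not have to mean drug-treated. Section 1.3.1.7 says that "different adhesives or 'under-taping' (such as with IV 3000, Tegaderm, etc.) will be tried", with medication mentioned only as a possibility.

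Other 6.2.2 criteria narrow the gap. A severe reaction is reportable anyway if it is an SAE (item 1), is tied to a study procedure (item 3), interrupts device use (item 4), affects study procedures (item 5) or leads to an emergency department visit (item 6).

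**Infusion-set site.** The 6.2.2 skin sentence is silent and item 2 defers to 6.3, so there is no direct contradiction. The last 6.2.2 criterion, which includes "insulin exposed to high temperature that loses potency), signs or symptoms related to insulin" infusion, has no drug condition and may bring some of these reactions back in. The text does not say whether it does.

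**2. What one such event does to the any-AE rate.**

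Inputs: 30 completers as the goal and at most 45 enrolled (2.1); 8 weeks plus the 3-day contact (3.1); up to 28 days from consent to the end of screening and 10 more to pump initiation (2.4); events counted from enrollment to the earlier of the post-study contact and day 71 after initiation (8.5). The denominator of the rate is not defined. I assume that it follows the event window and show a range.

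Person-years = participants × days / 365.25. Shift per event = 100 / person-years.

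- Short: 30 × (56 + 3) = 1,770 days; 1,770 / 365.25 = 4.85 person-years; 100 / 4.85 = 20.6 per 100 person-years.
- Long: 45 × (28 + 10 + 71) = 45 × 109 = 4,905 days; 4,905 / 365.25 = 13.43 person-years; 100 / 13.43 = 7.4 per 100 person-years.

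The short case leaves out the time between enrollment and pump start. The long case has all 45 start the pump and use every window in full. Both are outer illustrations.

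**The case against.** The best defence is that the sections can be read together. The 6.2.2 sentence says when a sensor reaction may be reportable and does not say that every such reaction must be. The duty to report comes from the numbered criteria; item 2 and the ADE definition both defer to 6.3; and any reaction that needs a drug also meets the 6.2.2 condition. On this reading 6.3 is simply the stricter rule and controls. That reading is possible. But it leaves the severity limb of the 6.2.2 sentence with no effect for ADEs, and it lets a severe sensor reaction go unrecorded. A site that takes the specific sentence at face value is not misreading the protocol. It is also unsettled whether a sensor reaction is an ADE at all: 4.1 names only the portal and the pump as investigational components, while 6.3 treats sensor reactions as ADEs.

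Several parts of the defence stand in full. Nothing in the protocol calls a changed adhesive, under-taping or site rotation treatment, so a reader who infers that every mild reaction falls into the conflict goes too far. Items 3 to 6 will catch many severe reactions. The Medical Monitor reviews each AE form, which helps against over-reporting, though not against an event never entered.

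A reader might also assume that, say, 10% to 20% of the children have a discordant reaction and multiply up to a large shift in the rate. The documents give no incidence. They also require recent Dexcom use (2.2, criterion 4) and exclude known, ongoing adhesive intolerance (2.3, criterion 9), both of which point to fewer sensor reactions.

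**Conclusion.** The inconsistency is real and lies in the current text, but it is narrow. It clearly affects a severe sensor-site reaction managed without a drug that meets no other 6.2.2 criterion. It affects a milder reaction only if non-drug measures count as treatment. For infusion-set reactions the problem is an unstated rule, not a contradiction.

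Each discordant event moves the any-AE rate by roughly 7 to 21 per 100 person-years under the person-time assumptions above, and moves the ADE count by one if the reaction is classed as an ADE. The number of such events cannot be estimated from the documents.

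Two stronger inferences are not supported. One is that counts from different sites could not be pooled: different practice is possible, but the documents do not show that it occurs or how much it would matter. The other is that the primary results are at risk: the two outputs are tabulated without a hypothesis test, and the CGM endpoints and their testing hierarchy are untouched. The point is worth fixing because the fix is cheap and a missed event cannot be recovered from the database.

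**What to change.** Put one identical rule in 6.2.2 and 6.3, covering sensor and infusion-set reactions alike. For example: a skin reaction is reportable if it is rated severe, if it required pharmacologic treatment, or if it meets another 6.2.2 criterion; otherwise it is not. This replaces both the 6.2.2 skin sentence and the 6.3 exception, and it removes the question of whether under-taping is treatment. State whether the insulin-infusion criterion is meant to cover infusion-site skin reactions.

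Send sites a memo with the rule. Before the ADE table is produced, ask them to check visit records for severe skin reactions that were not entered, and check entered events against the same rule. The cost is a wording amendment with IRB review, the memo, and a few more AE and Device Issue forms. No analysis changes.
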